During this study we will: 1) Conduct a pilot test with WWIDs (n=68) randomized to either a “Basic” or “Enhanced” intervention. Women randomized to the “Basic” group will receive general PrEP counseling from the study physician and PrEP counselor at Prevention Point, general written materials, as well as “general” reminder text messages for appointments. Those in the “Enhanced” group will receive targeted counseling by a trained PrEP counselor who will emphasize the targeted messages, doctor counseling, customized written materials, as well as supportive targeted text messages and reminders. Targeted messages and materials are informed by our formative findings. Both groups will get assistance with making their doctor appointments and will have PrEP dispensed at Prevention Point’s medical clinic. 2) To assess promise of efficacy, we will compare PrEP adherence (biomedical testing, self-report) as primary outcomes at one month, end, and three-month follow-up. We will compare changes to self-efficacy, decisional conflict, and PrEP perceptions as secondary outcomes. To assess feasibility and acceptability we will compare attitudes about the intervention, prescription pick up, and number of text messages opened. Figure 1 illustrates the study design:

Figure 1. RCT Study Design

**HIV- WWIDS
(n=68)(randomized)**

“Basic” Group

- General PrEP counseling by study physician and PrEP counselors at PPP
- General written materials on PrEP
- Assistance with medical appointments
- Prescription pick-up at PPP
- General text message reminders of appointments

“Enhanced” Group

- General PrEP counseling by study physician and targeted PrEP counseling by trained counselor
- Targeted materials based on formative findings
- Assistance with medical appointments
- Prescription pick-up at PPP
- Targeted supportive text messages and reminders

Randomized Pilot

We will recruit and enroll 68 WWIDs from syringe exchange who consent to participate in the intervention and will be randomly assigned to either the “Enhanced” or “Basic” group. Both groups will participate for six months (three months in the intervention and a three month follow-up), receiving PrEP counseling at Prevention Point (intervention monthly; control as requested by the participant), educational materials (targeted vs. general) and PrEP reminders via text messages (intervention also receives supportive messages about PrEP use). They will

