Participants will also continue to be monitored by the physician at Prevention Point. It is expected that a blood test or urine sample measuring PrEP levels and an HIV screening test would be done at the beginning, mid-point and the end of the intervention. It will also be done three months after the intervention is over. This will provide biomedical adherence data and ensure that participants have remained HIV negative.

After the intervention is over, all study participants may continue their PrEP prescription and have it administered out of the medical clinic at Prevention Point. In addition, PrEP counselors will remain available for participants should they have any further questions. Specialized counseling and text messages will no longer be provided. Three months after the intervention is over, we will contact participants to complete the last study assessment. This will be done at Prevention Point when the participant is there.

Instruments

There are five study assessments (See attachments). They include:

1. Eligibility Screener
2. Baseline Assessment
3. Mid-Intervention Assessment (in person and one question via text)
4. Post-Intervention Assessment
5. Three month follow-up Assessment

Analysis Plan

General - All data will be graphed and tabulated by treatment group for review of distributional properties and anomalous values prior to the main analyses. Continuous and normally distributed variables will be summarized with means and standard deviations. All parameter estimates will be bound by 95% confidence intervals and tests for differences in means and proportions will be deemed statistically significant $p < 0.05$. Post-hoc tests of significance will be based on adjustments for alpha to protect family-wise error rates at 5% using the method of Benjamini & Hochberg. For all analyses described in this study, we will use Statistical Analysis Software (SAS, version 9.4, Cary, N.C.).

Primary Outcome. The study's intent is to provide directional insight into the design of subsequent programmatic studies. As such, univariate group comparisons will be accomplished using an independent two-sample t-test for continuous measures (or non-parametric Wilcoxon

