statistic if the data is non-normally distributed) and chi-square test for categorical measures (or Fisher's Exact test if appropriate). Blood test results will also be compared to adherence benchmarks for Tenofovir-Emtricitabine and categorized as a binary variable (yes/no) based upon the mean value observed by all patients, with data at one month, three months and three months post intervention. We will use ANCOVA to assess differences between self-reported adherence and adherence as measured by blood test in the treatment group. Primary efficacy analyses will be a comparison of experimental to control group at one month, three months and three months post intervention, while other subgroup analyses based on race/ethnicity or age, for instance, as well as potential mediators and moderators, will be considered post-hoc exploratory analyses. In addition, logistic regression modeling will be used for binary adherence measures to assess group differences. Model assumptions will be tested, including linearity between the logit of the independent variables and the dependent, multicollinearity, and model misspecification.

Secondary outcomes. Secondary outcomes include self-efficacy, PrEP attitudes and decisional conflict. These measures are all continuous. Following evaluation of the primary outcome, we will explicitly examine the association between treatment adherence characteristics and extent of change among individuals in the treatment conditions in order to evaluate dose-response associations. Multiple linear models will be used to examine relationships between the groups and decisional conflict scale items, self-efficacy, and PrEP attitude scales at month three and three months post intervention. In these models, baseline outcome measures will be adjusted as covariate in the model development. PrEP attitudes will also be assessed through perceptual mapping analysis and compared from baseline to three month and three month follow-up for each group to assess "movement" toward adherence and away from negative perceptions of PrEP use. Promise of efficacy would indicate more movement by those in the "Enhanced" group compared to the "Basic" group. We will also explore potential mediators and moderators (HIV stigma, depression, level of drug use, social support). Outliers will be assessed using standardized residuals; if necessary, analyses will be accomplished for all data as well for non-outlying cases only.

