All participants will give informed consent to participate in the project and HIPAA consent to have access to health-related information. They will sign a PPP HIPAA consent that allows Project PEACE study staff to have access to their HIV test result, adherence information, and other medical information pertinent to the study. The research staff will read, review, and discuss consent forms with all potential participants prior to asking them to acknowledge the consent. If the potential participant appears confused or indicates she does not understand the consent, the moderator will attempt to identify the misunderstanding and to explain the consent again. If the potential participant still does not comprehend the consent, she will be excluded from the study. We will confirm that potential participants understand the material covered in the consent procedure by asking questions prior to asking the person to sign the consent form. These will include open-ended (e.g., "Could you tell me what's going to happen if you enroll in the study?") and closed questions (e.g., Will you get free medications as part of this research study?"). Responses that suggest confusion or inaccuracies that staff cannot successfully clarify will result in exclusion from the study and direction to appropriate outside referrals. If the participant agrees to participate, we will indicate this willingness on the REDcap project on a wireless tablet. We will provide a paper copy of the consents to the participant to take with her.

Provisions to Maintain the Confidentiality of Data

Assessment responses and all other data (e.g. % prescription pickups) will be entered into REDCap, which is protected behind Temple's firewall and HIPAA compliant. Each participant will be auto-populated with a study ID and no identifying information will be linked to the study record. Only the research staff will have access to, or be able to open, the REDCap database.

Risk to Participants

1. **PrEP use** - There are some risks to taking PrEP, including nausea, dizziness, headache and fatigue. These usually subside after a few weeks of taking the medication. The physician will assess each participant for appropriateness of taking PrEP and anyone who has counter indications will not be prescribed PrEP. They will also be monitored throughout the intervention by the medical staff at PPP to ensure that no one whose side effects may be damaging continues to take PrEP.

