G- END OF INTERVENTION SURVEY

H- THREE MONTH FOLLOW UP SURVEY

I – OUTCOMES AND SOURCE

Statistical Analysis Plan - Aim 3 Clinical Trial

General. All data will be graphed and tabulated by treatment group for review of distributional properties and anomalous values prior to the main analyses. Continuous and normally distributed variables will be summarized with means and standard deviations. All parameter estimates will be bound by 95% confidence intervals and tests for differences in means and proportions will be deemed statistically significant $p < 0.05$. Post-hoc tests of significance will be based on adjustments for alpha to protect family-wise error rates at 5% using the method of Benjamini & Hochberg. For all analyses described in this study, we will use Statistical Analysis Software (SAS, version 9.4,Cary, N.C.).

Primary Outcome. The study's intent is to provide directional insight into the design of subsequent programmatic studies. As such, univariate group comparisons will be accomplished using an independent two-sample t-test for continuous measures (or non-parametric Wilcoxon statistic if the data is non-normally distributed) and chi-square test for categorical measures (or Fisher's Exact test if appropriate). Blood test results will also be compared to adherence benchmarks for Tenofovir-Emtricitabine and categorized as a binary variable (yes/no) based upon the mean value observed by all patients, with data at one month, three months and three months post intervention. We will use ANCOVA to assess differences between self-reported adherence and adherence as measured by blood test in the treatment group. Primary efficacy analyses will be a comparison of experimental to control group at one month, three months and three months post intervention, while other subgroup analyses based on race/ethnicity or age, for instance, as well as potential mediators and moderators, will be considered post-hoc exploratory analyses. In addition, logistic regression modeling will be used for binary adherence measures to assess group differences. Model assumptions will be tested, including linearity between the logit of the independent variables and the dependent, multicollinearity, and model misspecification.

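### The only stated yes/no rule for blood adherence is the pooled sample mean, not the benchmark named beside it, so the adherent share does not measure adherence

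*Combined protocol and SAP*

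**What the plan says.** Study Design makes adherence primary: "we will compare PrEP adherence (biomedical testing, self-report) as primary outcomes", at one month, end of intervention and three-month follow-up.

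The Primary Outcome paragraph of the protocol's Analysis Plan, repeated in the Statistical Analysis Plan - Aim 3 Clinical Trial, has one sentence on the blood variable. It begins "Blood test results will also be compared to adherence benchmarks for Tenofovir-Emtricitabine" and goes on to say that results are "categorized as a binary variable (yes/no) based upon the mean value observed by all patients". No benchmark value, unit or source is given in either place.

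The same paragraph says that "logistic regression modeling will be used for binary adherence measures to assess group differences" and provides chi-square or Fisher tests for categorical measures. It also provides an analysis that needs no cut: "univariate group comparisons will be accomplished using an independent two-sample t-test for continuous measures", or Wilcoxon if the data are not normal.

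Three other places bear on the point:

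- The Privacy section has the study coordinator take adherence from the health record and enter it in REDCap as 0 for no and 1 for yes, with no threshold.
- Procedure Phase 3 allows "a blood test or urine sample measuring PrEP levels". Its one-month text question, also answered 1 or 0, is self-report and sets no blood threshold.
- The attachment list includes Attachment I, "OUTCOMES AND SOURCE", which is not in the text available.

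**The concern.** A reader expects an adherent woman to be one whose drug level reaches a value that indicates regular dosing. The stated rule instead asks whether her level exceeds the average of the women who happened to be in the trial, in both arms together. Two things follow from the definition alone:

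- A group in which everyone takes every dose still has many women below its own mean, and they are labelled non-adherent.
- If Enhanced women improve, the cut rises, and a Basic woman can change from yes to no with her own level unchanged.

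The harm is to the meaning of each arm's adherent share. The pilot exists to inform a fully powered trial, and that trial would need this share for planning. The share also cannot be set beside other studies, because the cut belongs to this sample. The text does not say whether the mean is taken per visit or over all visits. If it is per visit, a fall in adherence in both arms could be hidden because the cut falls too.

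**Working it through.** **What the plan supplies.** It gives no figure for the cut or for expected adherence, so there is no stated result to reproduce. The only input taken from it is 25 women per group (power paragraph). The rest is assumed, for illustration:

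- Adherent women's levels are lognormal with median 1 (the full level) and CV 50%.
- Non-adherers are at zero drug. This is plausible for some women, since "anyone who has counter indications will not be prescribed PrEP".

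**Formulas.**

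- Log-scale variance: ln(1 + 0.5²) = 0.2231, so SD = 0.472.
- Mean level of adherent women: exp(0.2231/2) = 1.118.
- Expected cut: overall true adherence × 1.118.
- Labelled share of an arm: its true adherence × Φ(−ln(cut)/0.472).

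**Labelled shares.**

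1. Everyone adherent: cut 1.118; Φ(−0.236) = 0.407, so about 41% are labelled adherent.
2. Both arms at 50%: cut 0.559; 0.50 × Φ(1.231) = 0.50 × 0.891 = 0.445.
3. Basic 50%, Enhanced 90%: overall 70%, cut 0.783; Basic is 0.50 × Φ(0.519) = 0.50 × 0.698 = 0.349.

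Simulation (40,000 trials per scenario, with the cut recomputed in each) gives 41%, 44% and 35%. A fixed cut at 35% of the full level labels about 49% of Basic in both the second and third cases.

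**Sensitivity.**

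- For CV 30%, 50% and 80%, the all-adherent share is 44%, 41% and 37%. Basic's share falls from 49% to 42%, 44% to 35%, and 37% to 28%.
- With non-adherers at 10% of the full level (CV 50%), Basic falls from 42% to 33%.
- At low adherence with non-adherers at zero, the labelled share is close to the truth (true 10%, 20%, 30%: labelled 10%, 20%, 29%). With non-adherers at 10% of the full level it is 18%, 21%, 29%.
- Under normal levels with CV 25%, the mean rule labels about 50% adherent whether both arms sit at 0.3 or at 2.0 times a benchmark. The benchmark itself would give about 0% and 98%.

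**Power (uncorrected chi-square, 5%, non-adherers at zero, CV 50%).**

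| True rates | Mean cut | Fixed cut 35% of full level | Fixed 70% | Fixed 100% |
|---|---|---|---|---|
| 50% vs 90% | 58% | 89% | 65% | 33% |
| 20% vs 60% | 84% | 86% | 70% | 45% |

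The mean cut can have less or more power than a fixed cut, depending on where the benchmark lies.

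**False positives.** With equal arms at true rates from 10% to 100%, the mean cut rejects in 5-7% of trials.

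**The case against.** The best case for the plan has three parts.

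**Intent.** The sentence names benchmarks first. The 0/1 entry described under Privacy cannot be made with a mean-based label until every level is known, which suggests that a fixed rule may have been intended. Attachment I may define one. This stands as a limit on what can be said about intent. It does not rescue the wording: an analyst who follows either analysis section would program the sample mean, and a cut in the attachment would then contradict them.

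**Pilot status.** The study seeks directional insight and says it is not fully powered. That is fair, but an interpretable adherent share per arm is part of what a pilot should hand to its successor.

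**Limited reach.** The pooled cut treats the arms alike, and other adherence analyses remain. This also stands, and it rules out three stronger readings that a reader might infer:

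- *The mean rule costs power.* The documents give neither a benchmark value nor an expected adherence rate, and the power table shows the sign changing with the assumed cut. A large loss appears only when the fixed cut is placed well between adherent and non-adherent levels.
- *The rule produces false positives or favours Enhanced.* Rejection with equal arms stays near nominal.
- *The whole primary outcome fails.* Self-report and the continuous comparison of levels do not use the cut.

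**Conclusion.** The point holds as a defect of definition. As written in both analysis sections, the yes/no blood variable does not measure adherence, and each arm's share depends on the other arm's levels. That conclusion needs no model.

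Its size does. Under the stated assumptions, full adherence is reported as about 41%, and Basic at a true 50% drops from 44% to 35% labelled when Enhanced goes from 50% to 90%. At true rates of about 10-30% with non-adherers at zero drug, the label happens to be nearly right. The documents do not say which case applies.

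No conclusion on power is supported, and the importance of the point does not rest on it. The 0/1 entry under Privacy and the mean rule are also inconsistent in practice and must be reconciled. The one reservation is Attachment I, which could contain a cut.

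**What to change.** In the Primary Outcome paragraph of both the Analysis Plan and the Statistical Analysis Plan:

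1. Delete the clause that bases the yes/no variable on the mean of all patients.
2. Classify each sample against the benchmark that the sentence already names. State its value and source, and fix both before outcomes are examined by arm.
3. Use the same benchmark at every visit, and make it specific to blood or urine.
4. Keep the numeric level and specimen type in REDCap, align the Privacy text with this, and report the planned continuous comparison alongside the binary one.
5. Check Attachment I and make it agree.

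The cost is wording and two retained data fields, with no extra samples or visits. The reported adherent share may change. Power for the binary comparison may fall if the benchmark lies close to the levels of either poor or good adherers, which is a further reason to report the continuous comparison with it.

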also complete surveys at the start of the study, at the one-month mark (mid intervention), the three month mark (end of intervention) and three months after the intervention is complete (follow up). Demographic information will be collected along with perceptions of PrEP, decisional conflict, and self-efficacy. Other moderators will also be collected. Compliance with PrEP will be assessed through self-report (in person and via text) and through either blood test or urine sample at one month, three months and six months. For recruitment and study timeline, see attachment A.

Study Timeline

We plan to begin the pilot RCT as soon as Institutional Review Board (IRB) approval is granted. We anticipate enrollment to take place between July through November, 2020 with follow-ups completed by March, 2021.

Inclusion/Exclusion Criteria

All participants must be self-identified women, 18 years of age or older, able to read and speak English, be HIV negative, self-report HIV risk behavior, report never taking PrEP, have a cell phone that accepts text messages, and must be a client of Prevention Point Philadelphia. They will also have to have health insurance (i.e. Medicaid). Individuals with mental illness that interferes with cognitive understanding or ability to provide informed consent will be excluded, with researchers trained to identify participants who exhibit signs of inability to meaningfully participate.

Inclusion Criteria

1. Woman-identified HIV negative client of Prevention Point Philadelphia
2. 18 of years of age or older
3. Self-report either sharing needles or having unprotected sex in the last 3 months
4. Speak and read English
5. Not have used PrEP previously
6. Have a working cell phone that receives text messages
7. Have health insurance

Recruitment

For this phase, we will recruit participants who are self-identified female clients of Prevention Point Philadelphia. Because Prevention Point received funds from the city, this protocol has also gone through review at the City of Philadelphia and been approved (see attached).

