Mosio will have no identifying information other than a participant’s phone number. Mosio will collect user data on the number of participants who open the text messages and will also resend text messages if they remain unopened for more than two days to assess feasibility. In addition, participants will be provided the opportunity to engage with study personnel if they have questions. A phone number will be provided in every text and study personnel will be available to take participant’s phone calls and answer their text messages. All messages/calls are sent to the study coordinator’s email and we will provide language that indicates that if questions are after business hours of 9 am to 5 pm we will answer the question the next morning. There will also be an opportunity to provide feedback. At mid-intervention participants will be asked to text back an answer to an adherence question. This provides an opportunity for participants to be actively engaged and to assess feasibility and acceptability. We will receive weekly reports from Mosio on which participants have opened text messages to assess feasibility.

At the end of the first month, all participants will also receive a text asking about their adherence to PrEP. They will respond with a 1 or 0 to indicate they have or have not taken PrEP the previous day. To help alleviate any problems with running out of cell phone minutes, every participant will receive a \$25 gift card to help pay for minutes needed. If they lose or have their cell phone stolen, we will assist them in getting a new one through the current services at PPP.

PPP has a current service that provided assistance to clients and we will work with them to help the study participant.

At the end of the first month we will also contact participants about completing a quick assessment of adherence and acceptability of the intervention. This will be done in person at Prevention Point. Similarly, at the end of the three-month intervention study staff will contact participants about completing a post-test assessment. We will attempt to correspond assessments to be at a time when they are already at Prevention Point and ideally meeting with their PrEP counselor or there for other services.

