Participation may contribute to increasing participants' initiation and adherence of PrEP, which will lower their HIV risk. Participation also may help participants consider how perceived stigma impacts their feelings about PrEP and help "normalize" the use of HIV prevention within the IDU community. The risks of discomfort or embarrassment discussing HIV and PrEP are reasonable in relation to the anticipated direct benefits to the subjects and the contribution subjects can make to society by reducing HIV stigma among WWIDs and encouraging HIV prevention efforts among their peers.

Privacy

As noted, all data will be coded to protect the confidentiality of participants. Only the Principal Investigator and the study coordinator will have access to the list of actual participant names and cell phone numbers. That list will be kept in a locked file (hardcopy only) in the office of [name]. The REDCap dataset with the coded data, with names removed, will be stored behind the firewall of Temple University. Medical information (adherence, HIV tests etc.) in medical charts will not be removed from Prevention Point. The study coordinator will access this through Prevention Point's electronic health record and note findings in the de-identified REDCap

database that will assign an ID number for each participant. Information will be entered into REDCap as coded data (i.e. adherence is coded 0 as no, 1 as yes). The PrEP counselors will know the names of the participants, but they will not have access to the REDCap database or participant medical records. The research assistant will only have access to de-identified data.

Compensation

Participants will receive up to a total of \$175 in gift cards. These incentives will be provided for different steps of the research study. Compensation will not be provided to those who drop out of the study or do not complete the step. Compensation will be broken down as follows:

- \$5 for conducting the eligibility screener and HIV test
- \$15 for completing the baseline test
- \$40 for meeting with the PrEP counselor (Up to four times, \$10 each time)
- \$15 for doctor visits (three times, \$5 each time)
- \$10 for completing one-month survey
- \$20 for completing three month survey
- \$50 for completing three month follow up survey
- \$20 for cell phone minutes

References

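### The ANCOVA planned to compare self-reported with blood-measured adherence ignores that both are taken on the same women; a within-woman comparison against a fixed benchmark would answer the question directly

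*Combined protocol and SAP*

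**What the plan says.** The Primary Outcome paragraph of the protocol's Analysis Plan contains one sentence on this comparison, and the Statistical Analysis Plan for Aim 3 repeats it word for word: "We will use ANCOVA to assess differences between self-reported adherence and adherence as measured by blood test in the treatment group". It names no dependent variable, factor, covariate, visit or pairing term. No paired or agreement method appears elsewhere in either text.

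The other relevant statements are:

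- **Same women.** Under Randomized Pilot: "Compliance with PrEP will be assessed through self-report (in person and via text) and through either blood test or urine sample at one month". The sentence goes on to three and six months.
- **Role of self-report.** Under Study Design: "we will compare PrEP adherence (biomedical testing, self-report) as primary outcomes at one month, end, and three-month follow-up".
- **Scale of self-report.** Procedure Phase 3 describes a month-one text: "They will respond with a 1 or 0 to indicate they have or have not taken PrEP the previous day". An in-person assessment takes place at the same time. The survey items are in attachments that are not part of the text available here.
- **Scale of blood adherence.** The Primary Outcome paragraph says that results are compared with adherence benchmarks for the drug and also "categorized as a binary variable (yes/no) based upon the mean value observed by all patients".
- **Covariates.** Baseline adjustment is stated only for the secondary-outcome models. The inclusion criteria require no previous PrEP use, so there is no earlier adherence value to serve as the usual ANCOVA covariate.

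**The concern.** The stated target is a difference between two measures of the same quantity on the same woman. That is a paired problem. ANCOVA as named does not lead to a paired analysis, and the two most direct ways of running it each miss part of the target. One gives an association. The other gives the gap with a standard error that ignores pairing. A separate difficulty arises if the yes/no blood variable enters: a cut at the sample mean does not say whether a woman reached an adherence level, so self-report would be compared with something other than adherence.

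What is at stake is the reading of self-report, which is one of the primary outcomes. The study's stated intent is to "provide directional insight into the design of subsequent programmatic studies", and how far self-report departs from drug level is useful for that. Counselling outreach and text content differ by arm, so misreporting could differ too, although nothing in the documents shows that it does.

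**Working it through.** The documents give no figure for this ANCOVA, so there is none to reproduce. The number of pairs comes from Sampling and the power paragraph: 68 × 0.75 = 51, planned as 50, or 25 per group. (The power statement for the arm comparison, 80% at an effect size of 0.79 with 25 per group, reproduces at 79.8% by the normal formula and 78.1% by the noncentral t.) Fewer pairs are possible, since a physician must first find PrEP appropriate, so 15 pairs are shown as well. All rates, correlations and distribution shapes below are assumptions.

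**1. One measure regressed on the other.** Let half the women be adherent by blood. Let o be the share of non-adherent women who report adherence, and u the share of adherent women who deny it. With Pb and Ps the two yes rates and P11 the rate of yes on both, the correlation is (P11 − Pb·Ps) / √[Pb(1−Pb)·Ps(1−Ps)].

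- o = 0.60, u = 0: Ps = 0.80 and P11 = 0.50. Correlation = (0.50 − 0.40)/√(0.25 × 0.16) = 0.50. Gap = 0.80 − 0.50 = 30 points.
- o = u = 0.25: Ps = 0.50 and P11 = 0.375. Correlation = (0.375 − 0.25)/0.25 = 0.50. Gap = 0.

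The correlation is the same with gaps of 30 points and zero. In 20,000 simulated trials of 25 pairs, the association was significant in 78% and 72% respectively. A test of association therefore cannot tell these two cases apart.

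**2. Method as a factor, no term for the woman.** With equal SDs and correlation ρ, the point estimate equals the paired one. The ratio of interval widths, unpaired to paired, is t(2n−2)·√2 / [t(n−1)·√(2(1−ρ))]. For n = 25 this is (2.011/2.064)/√(1−ρ) = 0.974/√(1−ρ).

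| ρ | n = 25 | n = 15 |
|---|---|---|
| 0.3 | 1.164 | 1.142 |
| 0.5 | 1.378 | 1.351 |
| 0.7 | 1.779 | 1.744 |

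At ρ = 0 with n = 25 the ratio is 0.974, so nothing is lost. At ρ = 0.5 the unpaired test's true type I error is about 0.6% instead of 5% (normal approximation), so the error is conservative.

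For binary data with o = 0.60, u = 0 and 25 pairs:

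- Unpaired half-width: 2.011 × √[(0.25 + 0.16)/25] = 0.257.
- Paired half-width: 2.064 × √[(0.30 − 0.30²)/25] = 0.189.

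That is 26 against 19 points.

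**3. Blood cut at the observed mean.** For a log-normal level the share above the mean is 1 − Φ(SD/2), where SD is on the log scale: 1 − Φ(0.25) = 40%, 1 − Φ(0.50) = 31% and 1 − Φ(0.75) = 23% at log SD 0.5, 1.0 and 1.5. The median drops out, so doubling every woman's level leaves the yes rate unchanged. If 70% truly meet the benchmark and all report truthfully, the false gap is 70 − 40 = 30, 70 − 31 = 39 or 70 − 23 = 47 points. At log SD 1.0 it runs from −1 point when 30% meet the benchmark to 59 points when 90% do.

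**4. Which between-arm summary to use.** With no under-reporting, the between-arm difference in gaps is (1−b1)·o1 − (1−b0)·o0, where b is true adherence, 1 is Enhanced and 0 is Basic.

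- Over-reporting 60% vs 30%, adherence 50% in both: 0.30 − 0.15 = +15 points.
- Over-reporting 30% in both, adherence 60% vs 40%: 0.12 − 0.18 = −6 points.
- Over-reporting 60% vs 30%, adherence 65% vs 50%: 0.21 − 0.15 = +6 points.

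The raw difference in gaps moves with true adherence, so it does not isolate misreporting. The over-reporting rate among women below the benchmark does.

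**The case against.** The strongest reply is that this is one supportive sentence in a pilot that is openly not fully powered, and that a competent analyst would fit a sensible model. The plan does not say that pairing will be ignored. If it were ignored, the error would be conservative under positive correlation. Nor does pairing guarantee power for binary data: under 60% over-reporting, exact McNemar against the unpaired model gives 81% vs 68% with 25 pairs, 46% vs 47% once 10% under-reporting is added, and 28% vs 37% with 15 pairs. All of this stands. It limits the point to precision and clarity of target, and it sets the severity.

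The mean cut matters only if the yes/no blood variable is used here. The same sentence of the plan also mentions benchmarks, so the sponsor may intend those. That is a fair reading, but the text as it stands gives the mean as the basis of classification.

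Three stronger readings are tempting, and the documents do not support them.

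- **That an arm coefficient from this ANCOVA generally mixes misreporting with true arm differences.** It depends on direction and on how reliable the blood measure is. In the three scenarios of step 4, in order, blood on arm plus self-report gives −0.11, +0.09 and −0.01. Self-report on arm plus blood gives +0.15, 0.00 and +0.13, which does separate the two when blood is error-free. The sentence also refers to the treatment group in the singular, which favours a single-arm analysis. The General paragraph uses the term for both arms ("All data will be graphed and tabulated by treatment group for review of distributional properties and anomalous values prior to the main analyses"), so the scope should still be stated.
- **That self-report is known to be binary throughout.** The 0/1 coding described under Privacy concerns medical information taken from the clinic's record. Only the month-one text is a documented 0/1 self-report.
- **That the main trial result is at risk.** The comparison of arms on biomarker adherence is specified separately.

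**Conclusion.** The concern holds as a minor point about a supportive analysis. The planned ANCOVA either tests the wrong quantity (association) or estimates the gap without its pairing. In the second case the interval is 16% to 78% too wide for assumed correlations of 0.3 to 0.7 with 25 pairs, on a common scale with equal SDs, and there is no loss at zero correlation. If the mean-split blood variable is used, a false gap of 30 to 47 points can appear when 70% meet the benchmark and everyone reports truthfully. That range rests on the log-normal assumption and could be near zero in other settings. The randomised biomarker comparison does not depend on this ANCOVA. Only the interpretation of self-report is affected.

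**What to change.** Replace the ANCOVA sentence in both the protocol and the SAP with a within-woman comparison at one, three and six months, shown separately by arm with the number of pairs:

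- Both measures binary: cross-tabulation, paired difference in proportions with 95% CI, and kappa.
- Both continuous on a common scale: mean paired difference with 95% CI.
- Self-report 0/1 with a continuous drug level, or different scales: classify drug level by the fixed benchmark and self-report on a matching yes/no scale, then pair.

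For any yes/no blood variable, use the benchmark that the plan already mentions and not the observed mean, and state its value in the SAP.

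To compare misreporting between arms, report descriptively the over-reporting rate among women below the benchmark and the under-reporting rate among those at or above it, in each arm with 95% CIs. Also state whether the treatment group means one arm or both, which month-one self-report (text or in person) is paired, and how urine results enter.

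The cost is wording and a little more output. No new data are needed, because both measures are already planned in both arms. The intervals will be wide: if about 12 of 25 women fall below the benchmark and 60% of them over-report, the approximate half-width is 1.96 × √(0.6 × 0.4/12) = 28 points. The between-arm comparison should therefore stay descriptive.
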